Level 4 - maintaining behaviours and pushing further

PAM has been used as a measure of health-related self-efficacy in a relevant study of transition to adult care among adolescents with chronic disease utilizing a technology program.³² Hibbard et al.³³ reported on the relationship between increased patient activation and improved self-management.

The license with Insignia Health for the PAM Measure does have a data-sharing requirement for scoring purposes. This is necessary to score each survey as there is not a scoring algorithm or rubric that is a static formula.

Health Care Experience

Measure of Process of Care (MPOC) (family-centred care)³⁴

The Measure of Processes of Care (<https://canchild.ca/en/resources/47-measure-of-processes-of-care>) is a well-validated and reliable self-report measure of parents' perceptions of the extent to which the health services they and their child(ren) receive are family-centred. The original version of MPOC is a 56-item questionnaire; as of 1999 there is a shorter, 20-item version. MPOC has been used internationally in many evaluations of family-centred service. Parents/caregivers will complete the MPOC-20 at Baseline and 6-Months. Additional mixed methods questions related to satisfaction with service will be complement the information collected within the MPOC.

Newest Vital Sign³⁵

As a complement to our Baseline measures, we will include a health literacy measure called Newest Vital Sign (NVS) <http://www.pfizer.com/health/literacy/public-policy-researchers/nvs-toolkit>. It is appropriate for our population and research purpose and can be easily administered in 3 minutes. The NVS measures words and numbers, not just word recognition. Since the NVS was published in December

NOTE: CTO#1666 Amendment approved by HiREB on January 9, 2023. Target sample was 264 participants; however, we randomized 52 participants, and did not complete the full-scale RCT. Linking health card numbers with provincial administrative data is labour intensive and costly, and the small number would not provide meaningful results. As approved by ethics, we dropped the health economic outcome analysis (Health card number linking, Health Utilities Index (HUI), Resource Use Questionnaire (RUQ)) and destroy stored health card number data.

2005, it has appeared in more than 25 peer-reviewed studies. It has been used to assess health literacy in populations with varying age, among racial/ethnic minorities, and applied to a wide variety of health conditions. The NVS will allow us to describe our population at baseline and explore determinants of change in self-management, as well as tailoring the intervention in the knowledge translation phase.

Cost Utility/Cost Effectiveness

The measure of effectiveness used in the cost effectiveness analysis will be consistent with the primary outcome measures. Additional measures will examine health-related quality of life using the PedsQL™¹¹ and the Health Utilities Index (HUI)^{®10}. The use of a preference-based measure such as the HUI will permit the calculation of quality-adjusted life years (QALYs) for a cost-utility analysis.

*Health Utilities Index® (Hui2/3) Proxy-Assessed (health-related quality of life)*¹⁰

The HUI is a generic health status instrument developed in Canada for use with children and has been incorporated in numerous clinical studies as well as the Canadian Community Health Survey, allowing the generation of norms for most age groups.¹⁰ The HUI Mark II includes 7 attributes: Sensation, Mobility, Emotion, Cognition, Self-care, Pain and Fertility with each attribute divided into 3 to 5 levels. The HUI III includes 8 attributes: Vision, Hearing, Speech, Ambulation, Dexterity, Emotion, Cognition and Pain. Each attribute of the HUI III consists of 5 to 6 levels. The organization of attributes by level of functioning is referred to as the HUI classification system. The HUI II and III use the same questionnaire to map individual responses to classification levels. As the mapping is done at the analysis phase, there is no additional response burden for completing the HUI. A multi-attribute utility function is used to assign weights to each level for each attribute. The weights for each attribute are combined statistically to derive a single utility using a scoring formula. Separate pre-established and validated utility functions and scoring formulae exist for the HUI II and III. Since the attributes in the HUI II and III are structurally independent, the user can produce attribute scores, in addition to overall utility for a health state that range from 0 to 1. To reduce burden on youth participants in this study, we will use the Health Utilities Index® (Hui2/3) Proxy-Assessed which will be self-administered by parent/caregiver proxies. The completion time is 5-7 minutes.

*Resource Use Questionnaire (RUQ)*¹²

The RUQ¹² is typically an interviewer-administered questionnaire for parents of children aged 11 to 18 years. The original RUQ measures the family resource use of condition-related treatments, services and programs, as well as parent time losses and family out-of-pocket costs. It also documents condition-related government subsidies and funding that families receive. Resources measured include those delivered by a parent, by other providers (e.g. behavioural specialist) or a combination of both. In this project, we will use a modified subset of RUQ questions, self-completed by the parent/caregiver. We have also included some questions to capture information about serious illnesses during the study including information about hospitalizations, ICU admissions, etc.

Provincial Data on Use of Health Care Services

We will request consent to obtain youth participant's Health Card Number to answer questions about use of health services like physician office visits, visits to emergency rooms and hospitalizations during

NOTE: CTO#1666 Amendment approved by HiREB on January 9, 2023. Target sample was 264 participants; however, we randomized 52 participants, and did not complete the full-scale RCT. Linking health card numbers with provincial administrative data is labour intensive and costly, and the small number would not provide meaningful results. As approved by ethics, we dropped the health economic outcome analysis (Health card number linking, Health Utilities Index (HUI), Resource Use Questionnaire (RUQ)) and destroy stored health card number data.

the study period (between the time a participant joins the study up until March 31, 2021). Participants have the option of participating in the study without sharing the youth's Health Card Number. The Health Card Number will allow us to link the information provided in the study with provincial data regarding the participant's use of health services. We will work with appropriate organizations in each province (Alberta, Ontario, Quebec, New Brunswick, and Nova Scotia) to gain approval to access provincial Health Services Administrative Data repositories. Health care services data recorded in the provincial administrative databases will be linked deterministically to the study data using the Health Card Number, partial date of birth and sex.

STATISTICAL ANALYSIS:

We will use regression analysis to adjust for baseline function as a sensitivity analysis to address any residual imbalance from the randomization.

The analysis and reporting of the internal pilot phase and main RCT results will follow CONSORT guidelines²³⁻²⁴. Patient demographics and baseline outcome variables (both primary and secondary) will be summarized using descriptive summary measures. All analyses will be performed using SAS 9.4 (Cary, NC). Analysis will be intention to treat. The table below provides a summary of study objectives, corresponding outcomes, hypotheses and methods of analyses. For subgroup analysis we will use interaction test (interaction of subgroup variable with the treatment or intervention variable).

Table 1: Study Objectives, Corresponding Outcomes, Hypotheses and Methods of Analyses

Objective	Outcome	Criterion for Success	Method of Analysis
Primary: To determine whether the MyREADY Transition™ BBD App intervention will result in improved transition readiness	Primary: 
 Change in TRAQ self-management score from Baseline to 6 months. 	Intervention > Control	T-Test; p<0.05
	Secondary: 
 Change in TRAQ self-advocacy score from Baseline to 6 months. 	Intervention > Control	T-Test; p<0.05
	Secondary 
 Health care transition experience 	Individual semi-structured interviews	Qualitative Methods
Secondary: What is the effect of the MyREADY Transition™ BBD App intervention for	Primary: Population Health 
 Serious illness (hospitalizations, ICU admission questions from Resource Use Questionnaire 	Intervention > Control	T-Test for continuous outcomes Chi-square test

NOTE: CTO#1666 Amendment approved by HiREB on January 9, 2023. Target sample was 264 participants; however, we randomized 52 participants, and did not complete the full-scale RCT. Linking health card numbers with provincial administrative data is labour intensive and costly, and the small number would not provide meaningful results. As approved by ethics, we dropped the health economic outcome analysis (Health card number linking, Health Utilities Index (HUI), Resource Use Questionnaire (RUQ)) and destroy stored health card number data.

improving health and use of health systems?	
 • PedsQL™ Pediatric Quality of Life • Patient Activation Measure (PAM) (health-related self-efficacy) • TRANSITION-Q 		for hospitalization
	Secondary: 
 • Utilization MyREADY Transition™ BBD App 	User metrics built into MyREADY Transition™ BBD App intervention to assess the extent to which various components of the intervention are accessed	Descriptive
	Secondary: Cost utility/cost-effectiveness 
 • Health Utilities Index® (Hui2/3) • Resource Use Questionnaire 	Evaluate changes in patients' health in relation to changes in cost to assess if the intervention represents an efficient allocation of health care resources	Descriptive; Cost-effectiveness analysis with support from Child-Bright health economics network team
	Secondary: 
 • Achievement of health/life goals • Canadian Occupational Performance Measure (COPM) 	Intervention > Control	Paired Student t-tests to compare mean ratings for performance and satisfaction on the COPM scoring system (10-point scale) with > 2 points difference as clinically meaningful difference

Qualitative Data Analysis

In this study, individual interviews will be audio-recorded and transcribed verbatim. Data will be stored and managed electronically using NVivo® Version 11³⁶, a qualitative research data management

NOTE: CTO#1666 Amendment approved by HiREB on January 9, 2023. Target sample was 264 participants; however, we randomized 52 participants, and did not complete the full-scale RCT. Linking health card numbers with provincial administrative data is labour intensive and costly, and the small number would not provide meaningful results. As approved by ethics, we dropped the health economic outcome analysis (Health card number linking, Health Utilities Index (HUI), Resource Use Questionnaire (RUQ)) and destroy stored health card number data.

software program to facilitate the organization and coding of large quantities of data. Conventional content analysis ³⁷ will be used to code, categorize and synthesize the data to contextualize the analysis of the primary aim of the RCT. In addition, data related to usability of the App will be monitored and analyzed by the Research IT team at McGill to inform ongoing App development.

Health Economic Evaluation

Cost-effectiveness analyses will be conducted from the perspective of the provincial payer, as well as from the perspectives of society and the family, data permitting. Costing relates to the cost to develop and resources to support the intervention as well as resources used for treatment/management of participants' health conditions over the study. Health resource use data include things such as the intervention, physician services, rehabilitation services, emergency services, hospital admissions, and medications. We anticipate that the health economic evaluation in this project will be exploratory since we are engaging youth during the timeframe prior to transition. However, there will also be opportunity to explore provincial jurisdiction patterns. There may be interest to submit a proposal to follow up this cohort in the future once they have landed in adult care, which would give us more of an opportunity to explore these health economics questions.

A decision tree that models the comparison groups will be constructed. The model will include all relevant outcomes and events that may occur with each group throughout the study period. A 3% discount rate will be applied to outcomes and costs extending beyond one year. All measurement and analytic assumptions made for the base case analysis will be clearly stated. The mean cost per child and the mean effectiveness result per child for each group will be represented in an incremental cost-effectiveness ratio (ICER) -- the ratio of the difference between groups in mean cost per patient to the difference in mean effectiveness. Subgroups of patients based on baseline demographic factors may be analyzed separately, if appropriate. Extensive sensitivity analysis including probabilistic sensitivity analysis will be undertaken to test the robustness of the results to variations in underlying assumptions.

PATIENT ENGAGEMENT:

Patient-oriented research refers to a continuum of research that engages patients as partners, focuses on their priorities and ultimately improves the value of research. Under this model, patients and parents/caregivers with "lived experiences," together with health professionals, join researchers as members of the research team. Most importantly, what patients and parents/caregivers contribute is the sharing of their values and priorities. Doing so ensures that the research conducted is meaningful and will have impact on those most affected by its outcomes. The entire team collaborates to plan and conduct the research, and to disseminate its findings. Researchers, research staff, and stakeholders involved in this project are encouraged to participate in the CIHR training curriculum in patient-oriented research to forefront the meaningful engagement of key stakeholders throughout our project.

READYorNot™ Brain-Based Disabilities Trial is a patient-oriented project of CHILD-BRIGHT, a pan-Canadian research program generally aimed at optimizing physical and mental health of youth with BBD and their families. In the READYorNot™ Brain-Based Disabilities Trial, the MyREADY Transition™ BBD

NOTE: CTO#1666 Amendment approved by HiREB on January 9, 2023. Target sample was 264 participants; however, we randomized 52 participants, and did not complete the full-scale RCT. Linking health card numbers with provincial administrative data is labour intensive and costly, and the small number would not provide meaningful results. As approved by ethics, we dropped the health economic outcome analysis (Health card number linking, Health Utilities Index (HUI), Resource Use Questionnaire (RUQ)) and destroy stored health card number data.

App has been developed and evaluated to promote transition readiness (self-management and self-advocacy skills) in preparing youth for the transition from pediatric to adult health care.

In Part 1 of the project, Heath Information Technology (HIT) development was based on Agile Programming Best Practices.³⁸ This gave us flexibility and helped us to integrate feedback from researchers, research staff, as well as youth, parent/caregiver and health care stakeholders. The research team worked in partnership with PFAC to plan interviews, focus groups and other interactive testing activities to ensure the MyREADY Transition™ BBD App matches the needs and interests of youth. In Part 2 of the project, the PFAC will continue to collaborate and guide the research team in planning this RCT to study the MyREADY Transition™ BBD App in health care settings across Canada. Then, in the Part 3 of the project, patients, parents/caregivers and health care stakeholders will continue to be involved to ensure findings of the project are communicated in innovative and understandable ways, and can reach those who need it most. All partners will continue to work together to define future research directions.

Members of our team are working together with CHILD-BRIGHT's Citizen Engagement Council, Ontario SPOR Support Unit (OSSU) and Maritime SPOR Support Unit (MSSU) on some tailored content to be delivered online for all members of our project including researchers, PFAC, clinicians and the research staff who will be part of the RCT. The training is especially timely as we expand the group for the RCT, to give everyone a shared understanding of the partnership, and set the stage for engagement and interaction throughout the project.

DISSEMINATION AND KNOWLEDGE TRANSLATION (KT):

KT activities directed at the academic and stakeholder community will include presentations at scientific meetings, publications in academic journals and dissemination of teaching and training tools through patient associations, and patient and family advocacy groups. All participants will be given the option to receive a plain language report at the end of the study, after the RCT results have been analyzed. We will leverage CHILD-BRIGHT'S Knowledge Translation Program and our PFAC partners to find novel integrated and end-of-study KT strategies for patients, parents/caregivers and health care providers who participated in the RCT and beyond. After the completion of this RCT, our team will explore the potential to make the App more widely available.

REFERENCES:

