Usability testing aims to ensure that interactive systems are adapted to the users and their tasks and is considered a fundamental component of the user-centred design process.¹⁵ Throughout the development of the MyREADY TransitionTM BBD App, iterative cycles of participatory design sessions were used to elicit patient, parent/caregiver and health care provider feedback on elements of the tools

NOTE: CTO#1666 Amendment approved by HiREB on January 9, 2023. Target sample was 264 participants; however, we randomized 52 participants, and did not complete the full-scale RCT. Linking health card numbers with provincial administrative data is labour intensive and costly, and the small number would not provide meaningful results. As approved by ethics, we dropped the health economic outcome analysis (Health card number linking, Health Utilities Index (HUI), Resource Use Questionnaire (RUQ)) and destroy stored health card number data.

(i.e. to learn what was working, what wasn't, and where gaps existed). This rigorous process was instrumental in refining the App intervention prior to the start of the RCT, thus *enhancing the likelihood of success of the intervention itself*.

Internal Pilot Phase

The British Medical Research Council explicitly recommends the use of feasibility studies prior to Phase III clinical trials.¹⁶ In order to guide the planning and to *enhance the likelihood of success of our full scale RCT*, the first three months of recruitment will comprise an internal pilot phase. In this internal pilot phase, we will aim to recruit the first 12 patients in each of the four regions, up to 48 participants across all regions.

During the internal pilot phase, we will observe the study procedures and consider key implementation aspects such as recruitment (including refusal rates and screening process), multi-site coordination/collaboration (including communication, documentation and provision of support) and intervention uptake and adherence (including technical support needs among app users). The results will be used to refine and enhance the research design. The RCT will proceed with procedural modifications based on the findings of the internal pilot study and final study analyses will incorporate all data. As long as the alpha-level is controlled, internal pilot designs have, at most, a small adverse effect on the significance level and may greatly improve the power.¹⁷

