number of participants in each of two groups: intervention group (132) and control group (usual care) (132). Since participants will be recruited from only four regions, we will model the effect of region as a fixed effect rather than a random effect.¹⁸ This will allow region-specific intervention effects to be modelled (i.e. region by intervention interaction effects). If no region by intervention interactions are found, the interaction terms will be dropped from the model and we will estimate an overall intervention effect. Since the region by intervention interaction is unknown, we take a conservative approach with a sample size calculation that will enable detection of an intervention effect within each site. This will allow for a properly powered analysis of the site by treatment interaction. The primary outcome measure (Transition Readiness Assessment Questionnaire, TRAQ)⁹ has been validated on a sample of youth with congenital heart disease and in the absence of literature specific to BBD, we will base our sample size calculations on these findings. We anticipate a mean TRAQ self-management baseline score of 3.01 (SD 1.02) (out of a possible 5.0) as reported for youth (with congenital heart disease) without a transition intervention and an anticipated mean score of 4.0 at 6 months post-intervention resulting in a change score of 1 (i.e., 1 SD), with $\alpha=0.05$ and 90% power.¹⁹ Therefore, in each region, we will require 23 youth in each of the 2 arms (total of 46) x 4 regions = 184. Estimating 30% attrition, we will enroll 264 participants.

Inclusion Criteria

- Youth with chronological age between 15 and 17 years of age (i.e. before 18th birthday), in one of the four study regions, followed in pediatric care and for whom a discharge from pediatric care is planned but not for at least 6 months.
- A diagnosis of one of the following neurological BBD: autism spectrum disorder, cerebral palsy, epilepsy, spina bifida, or fetal alcohol spectrum disorder.
- Cognitive ability to provide informed consent and the ability to read and understand English or French
- Access to internet and a smartphone, iPad/tablet or desktop computer.
- TRANSITION-Q²⁰ score >40 (as a screen to define a minimum threshold for transition readiness based on our earlier work).

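### An interaction pre-test of unstated level chooses between an overall and a regional analysis, and the plan does not say how primary success is judged if an interaction is found

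*Combined protocol and SAP*

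**What the plan says.** The Sample section sets out the model: "Since participants will be recruited from only four regions, we will model the effect of region as a fixed effect". It adds: "This will allow region-specific intervention effects to be modelled". The choice of final model then depends on the data: "If no region by intervention interactions are found, the interaction terms will be dropped from the model", and an overall intervention effect is estimated in that case. The same paragraph justifies the sample size as "a sample size calculation that will enable detection of an intervention effect within each site", with 23 youth per arm in each region at alpha 0.05 and 90% power.

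Table 1 (Statistical Analysis) describes the same primary outcome, change in TRAQ self-management score from baseline to 6 months, in a different way. It names one t-test at p<0.05, with success defined as intervention better than control. It contains no region term, no interaction step and no region-level test.

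Four things are stated nowhere: the level at which an interaction counts as found, whether tests are one- or two-sided, any adjustment across four regional tests, and what counts as primary success once an interaction has been found.

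**The concern.** The Sample section offers two routes to a conclusion about the App and lets the data pick between them. If both can yield a positive primary result, each spends error, and the total exceeds the level of either. The two are also linked in an unhelpful way. With no true effect anywhere, a chance interaction is the situation in which at least one region tends to stand out, so an unadjusted look at four regions at that moment will usually find something.

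At stake is whether the 0.05 used for sizing and in Table 1 is the error rate of the primary claim. There is a second gap. If an interaction is found, the Sample section does not provide for an overall estimate, although the hypothesis under Study Aims is an overall comparison of App users with usual care.

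**Working it through.** **Inputs.** From the Sample section: four regions, 23 per arm per region, alpha 0.05, power 90%, an expected difference of 1 point, SD 1.02, attrition 30%. From Randomization: 1:1 allocation stratified by region. From Table 1: one t-test at p<0.05, intervention better than control. Assumed because the documents are silent: the pre-test level, two-sided testing, normal change scores with equal SD, and the success rule after an interaction.

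**The plan's own figures.** A two-sample t-test at two-sided 0.05 with difference 1, SD 1.02 and power 0.90 needs 22.9, so 23 per arm; power at 23 is 0.90. Then 23 × 2 × 4 = 184. Allowing for attrition, 46 / 0.7 = 65.7, so 66 per region, and 66 × 4 = 264. The stated figures reproduce, and they do so with two-sided tests applied separately in each region.

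**Error of the two-step rule with no App effect in any region.** Step one is the interaction F test on 3 degrees of freedom. If it is not significant, the overall effect is tested with region in the model. If it is significant, the four regional effects are each tested at 0.05 and any one counts as success. Then

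error = (1 − pre-test level) × 0.05 + pre-test level × P(any region significant, given a significant interaction).

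Simulation (400,000 null trials per setting, 23 per arm per region) gives the conditional probability as 0.935 for a pre-test at 0.05 and 0.81 for one at 0.10.

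- Pre-test at 0.05: 0.95 × 0.05 = 4.75%, plus 0.05 × 0.935 = 4.7%; total about 9.4%.
- Pre-test at 0.10: 0.90 × 0.05 = 4.5%, plus 0.10 × 0.81 = 8.1%; total about 12.6%.

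**Varying what the plan leaves open.**

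| Reading | Error with no effect |
|---|---|
| Single t-test of Table 1, or overall region-adjusted test alone | 5.0% |
| Interaction found, then the average effect tested | about 5.0% |
| Interaction found, then all four regions required | 4.7% |
| Any one region, pre-test 0.05, either direction | 9.4% |
| Any one region, pre-test 0.10, either direction | 12.6% |
| Any one region, pre-test 0.05, App's favour only | 5.1%, against 2.5% |
| Any one region, one-sided tests at 0.05, pre-test 0.05 | 8.3%, against 5% |
| Any one region at 0.05/4 = 0.0125, pre-test 0.05, either direction | 7.2% |

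The last row shows that adjusting only the regional tests does not restore 5%, because the overall route has already spent 4.75%.

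**At the size reached.** The document's note reports 52 randomised. Spread evenly, that is 52 / 8 = 6.5 per arm per region; the actual spread is not given. With 6 or 7 per cell and a 0.05 pre-test, the any-region rule gives 9.1% to 9.5% in either direction and 4.9% to 5.2% in the App's favour. The smaller sample leaves the inflation about the same.

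**The case against.** The strongest reply is that the success rule behind 9.4% is not in the documents. The Sample section says regional effects will be modelled; it does not say that one region at p<0.05 meets the primary criterion. Table 1 is the only place where a criterion is attached to a test, and there it is one t-test. On that reading the error is 5% and the regional modelling is supportive. This stands, and it means 9.4% cannot be given as the trial's error rate.

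The direction also matters. The 9.4% includes regions in which the App looks worse, while Table 1 counts only results in its favour. The directional comparison is about 5% against 2.5%, and the 2.5% is itself inferred from two-sided testing. This stands too, although the rate still doubles.

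A reader might infer that the inflation arises whichever model is primary, or that only favourable regions would be reported. The first is contradicted by the 5.0% rows above. The second has no basis in the text. Nor does the plan forbid an overall estimate after an interaction; it just does not call for one. The remark about alpha control under Internal Pilot Phase concerns internal pilot designs and has no bearing on the regional tests.

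The reply does not remove the ambiguity. The Sample section commits to a region model and a pre-test, Table 1 to neither, and nothing says which prevails. Sizing each region for its own test at 0.05 makes an inferential use of regional results a fair reading.

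**Conclusion.** The concern holds as a gap in specification with a conditional cost. A pre-test of unstated level selects the analysis, Table 1 describes a different one, and neither says how the primary hypothesis is judged when an interaction is found. Depending on how that gap is filled, the error runs from about 5%, with no inflation, to about 9.4% (pre-test 0.05) or 12.6% (pre-test 0.10). In the App's favour alone, with a 0.05 pre-test, it is about 5% against 2.5%. The upper figures rest on three assumptions: that any single unadjusted regional result counts as success, two-sided tests at 0.05, and equal regions with a common SD. The documents do not support a flat statement that the false-positive rate is 9%. They do leave the choice open until after the data are seen, and that is reason enough to settle it.

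**What to change.** Replace the pre-test rule in the Sample section with wording such as: *The primary test is the overall intervention effect on change in TRAQ self-management, adjusted for region, at two-sided 0.05, whatever the interaction test shows.* Amend the primary row of Table 1 to name the same test. Report the interaction and the region-specific effects with 95% confidence intervals as supportive, and state that no single-region result can meet the success criterion.

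This holds the error at 5.0%, reconciles the two sections, and guarantees an overall answer to the stated hypothesis. It costs a few lines of text and needs no new data or participants. The downside is that an effect confined to one region could not be claimed as primary success.
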